- For the rest of the Follow-Up Period (after the 1st CGM change) The family nurse will visit the patient every 3 days for the insulin cartridge refilling, catheter replacement, battery charge and for uploading data from the pump to the cloud-based t:connect® platform and every 9 days for CGM replacement. The family nurse will inquire about any event, make sure that it is reported in the patient diary and report to the investigator and/or HHP as appropriate.

The HHP will call the patient 5 days after his/her last visit (day 15) and then will visit the patient at home, at day 30 and day 60, for reminders on the automated insulin delivery system training and instructions on how to manage any trouble.

At each visit, and whenever needed, the HHP will review the data and will inform the investigator of any abnormalities. The HHP will make sure the patient reports any event and will notify the investigator of any event recorded.

For patients in the control group:

The family nurse will perform the usual care i.e. daily glycaemic controls and insulin injections. The family nurse will also make sure the patient is reporting any event in his/her diary.

The family nurse and HHP will visit the patient at home at day 70, to set up a CGM for 20 days blinded recording. The patient and/or caregiver will receive a training with reminders of the proper usage of the CGM.

5/ Ending Period:

All patients come to the investigator site at day 90 for final data collection and evaluation.

All patients will then return to their pre-study therapy.

Investigational Medical Device

The tested therapeutic strategy consists of an automated insulin delivery system and a tailored home healthcare provider service to ensure its proper use by the patient and family nurse. The automated insulin delivery system is made up of 2 medical devices, an insulin pump with a closed-loop algorithm, which is the Tandem t:slim X2 Insulin Pump with Control-IQ Technology (CE mark for T1D patients), and a CGM which is the Dexcom G6 system (CE mark).

Tandem t:slim X2 Insulin Pump with Control-IQ Technology "The Pump" is made up of:

- The t:slim X2 Insulin Pump and the t:slim 3mL (300 units) cartridge - The catheter (infusion set) which needs to be changed every 3 days.

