Patient selection is based on the selection, inclusion and exclusion criteria listed below. Patients who meet each of the selection and inclusion criteria and none of the exclusion criteria are eligible to participate in this study.

All patients will receive oral and written information on the study and will sign a written Informed Consent Form (ICF) prior to any study specific assessments and before any data collection is performed.

IV.1.1 - SELECTION CRITERIA

During the selection visit (V0) detailed in section VI.2, the investigator will check that study eligible patients meet all the following selection criteria:

- 1. Male or female patient aged 18 years or older,
- 2. Type 2 Diabetes diagnosed for at least 6 months with a stable authorized antidiabetic therapeutic regimen for 3 months,
- 3. Treated with insulin for at least 6 months,
- 4. Patient with 8.0% ≤ HbA1c <12.0% within the last 3 months before selection,
- 5. Patient with a current minimum of 2 daily insulin injections and who would benefit of an optimisation,
- 6. Patient requiring long term family nurse's daily assistance at home for performing insulin injections and/or glucose monitoring,
- 7. Total daily insulin dose < 1.5U/kg,
- 8. Patient willing and able to complete the requirements of the study,
- 9. Patient living with a caregiver or a diabetes care partner, or patient living alone but with a caregiver living nearby who has a telephone and a key to his or her home,
- 10. Patient living in an area covered by a GSM (Global System for Mobile Communications) network and not considering a trip outside of France or out of an area covered by a GSM network within the planned dates corresponding to the 30 days of the installation of the pump (to cover the open-loop period and first 15 days of the closed-loop period) and the last 20 days of the study.

IV.1.2 - INCLUSION CRITERIA

Before randomisation, the investigator will check that study eligible patients meet all the following inclusion criteria:

- 1. Patient having demonstrated ability to understand the benefits and harms of the automated insulin delivery system and to continuously and safely wear a CGM, as per investigator's judgement,
- 2. Family nurse having demonstrated ability to use the automated insulin delivery system, as per Home Healthcare Provider (HHP) judgement,

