The automated insulin delivery system allows automated glycaemia recording every 5 minutes and comparison to the pre-set target glucose range. The need for insulin subcutaneous infusion or carbohydrates consumption is automatically calculated if the glucose level rises above the pre-set glycaemia upper limit or drops below the pre-set glycaemia lower limit, respectively. If the upper limit is exceeded, the required amount of insulin is automatically delivered by the Pump. If the lower limit is dropped below, the required amount of carbohydrates to be ingested is indicated to the patient.

Insulin is not part of the automated insulin delivery system. The automated insulin delivery system is intended to be used with U100 Humalog® or NovoRapid® rapid-acting insulin analogues only. Use of insulin with lesser or greater concentration can result in under delivery or over delivery of insulin. This can cause a very high or a very low blood glucose.

V.1.1 - TANDEM T:SLIM X2 INSULIN PUMP WITH CONTROL-IQ TECHNOLOGY

This medical device consists of the Tandem t:slim X2 insulin pump with the Control-IQ algorithm system implemented to the pump.

The Tandem t:slim X2 Insulin Pump with Control-IQ technology package includes the following items:

- t:slim X2 Insulin Pump with Control-IQ Technology. The t:slim X2 Insulin Pump is made up of the t:slim X2 Insulin Pump (English product with units of insulin designated in mg) and the t:slim 3mL (300 units) cartridge.
- Pump Case.
- t:slim X2 Insulin Pump with Control-IQ Technology current user guide in English and the previous one in French with a summary of differences.
- USB Cable.
- Wall Power USB Adapter and plug adapter suitable for French electrical outlets.
- Cartridge Removal Tool.
- Assortment of infusion sets.

The infusion set will be changed by the family nurse every 3 days at the same time the cartridge is refilled.

V.1.1.1 - **CONTROL-IQ ALGORITHM SYSTEM**

The Control-IQ algorithm system is implemented in the pump. It includes automated insulin correction boluses for high blood glucose in addition to basal rate modulation and it has a dedicated hypoglycaemia safety system. The algorithm is initialized based on the patient's body weight and estimated total daily insulin dose. It calculates the required insulin infusion rate or suspends insulin delivery when low blood glucose is predicted, aiming at a predefined target glucose level by continuously adapting model parameters.

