For patients of the investigational group:

- The family nurse(s) will be trained to the use of the Tandem t:slim X2 with control IQ technology system and to the upload of data and to data visualisation on the t:connect® platform.
- The family nurse will administer the insulin bolus during his (her) visit at the patient's home
 using the Tandem t:slim X2 insulin pump as instructed during his (her) training. The frequency
 of the daily home nurse visit(s) will remain the same as for standard diabetes care during the
 initiation period.
- The family nurse will replace the catheter and refill the insulin cartridge of the Pump every 3 days at home.
 - The family nurse will change and replace the Dexcom G6 sensor every 9 days and upload the Dexcom G6 CGM and pump data on the cloud-based t:connect® platform.
- The family nurse will be reminded of the date of the next visit at the hospital and of the procedures to be performed until then.
- During each visit at the patient's home, the family nurse will ensure that any adverse events and device failure/deficiencies will be reported by the patient in his/her diary. The family nurse will immediately inform the HHP nurse of any adverse events or device deficiencies/failure occurring during the trial.

VI.4 - Run-In visit (V2)

The run-in visit purpose will be to finalize the installation of the automated insulin delivery system studied in the investigational group. Thus, this visit will be the starting point of the evaluation of the tested strategy CONFIDENTIAL Restricted- Clinical Investigation Plan version n° 7.0 – 04/03/2025 69 / 155

therapy. The run-in visit is performed at the hospital **for patients of the investigational group only**. It will consist in a 2-night hospitalization for the automated insulin delivery system to be initiated (closed-loop mode), the settings adjusted and the patient trained to the management of the automated insulin delivery system in closed-loop mode.

VI.4.1 - ROLES OF THE INVESTIGATOR

- The Investigator will be trained to the automated insulin delivery system in closed-loop mode and to the display and exploitation of data on the t:connect® platform.
- The Investigator will set up the automated insulin delivery system and define the settings based on insulin pump and CGM data collected during the initiation period, using the standard mode of the algorithm. The patient will be closely monitored to ensure the settings and mode chosen are safe.

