 - The HHP will visit the patient at home the day after the end of hospitalization (Day 3, visit 3) in the presence of the family nurse, the day of the first CGM sensor change (Day 9, visit 4), 1 month (Day 30, visit 6), and 2 months (Day 60, visit 7) after the set-up of the automated insulin delivery system in closed-loop mode.
 - In addition, the HHP will call the patient at Day 15 (Visit 5). The visits 3 to 7 and the phone call at day 15 are intended to:
 - o Ensure that the patient enters meal information in the Pump for bolus insulin delivery and knows how to do it.
 - Remind the patient of the management of alerts, alarms and emergency issues. The contact details of the persons to be contacted in case of safety or technical issues will be reminded to the patient. The HHP will ensure that adverse events and/or device deficiencies will be reported by the patient in his/her diary. Any mismanagement of the system will be reported to the Investigator.
 - Ensure that data are uploaded on the t:connect® platform and remind the family nurse of the procedures for data upload (performed twice a day with 6 hours minimum interval during the first 10 days following patient hospital discharge and at each visit afterwards).
 - In addition, the HHP will provide the patient every month with required supplies for automated insulin delivery system.
 - During the follow-up period, the HHP will also perform a remote follow-up of glycaemia and insulin data. Serious adverse events, non-serious adverse events possibly related to the IMD, to investigation procedures or to diabetes and device deficiencies/failure will be immediately notified to the Investigator.
- For patients of the control group (Visit 8):
 - An appointment for Visit 8 will be planned 20 days before the study end visit to set up a new Dexcom G6 system for a 20-day continuous glucose monitoring period. This visit will be performed with the family nurse.
 - The patient will be reminded of the precautions of use of the Dexcom G6 CGM, on management of emergency problems and device deficiencies/failure. The HHP will also

remind the patient of completing the patient diary, of the date of the next visit at hospital (Visit 9)

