• The HHP will configure the CLARITY® account and remind the family nurse of the process of data upload on the CLARITY® platform. The family nurse will also be reminded to check that the patient fills in the patient diary and to report any adverse event or device deficiencies/failure to the HHP.

| The HHP | will | complete | the | e-CRF |
|---------|------|----------|-----|-------|
|---------|------|----------|-----|-------|

VI.5.3 - ROLES OF THE FAMILY NURSE

For patients of the investigational group:

On Day 3, the family nurse will be trained by the HHP to the upload of data and to data visualisation on the t:connect® platform.

Specific vigilance during the first 7 to 10 days

[figure not shown]
From the first day after patient discharge (Day 3) to the day of first CGM sensor change, the family nurse will visit the patient at least twice a day at 6 hours minimum interval to ensure the patient uses the pump safely, to upload data from the pump to the t:connect® platform, to ensure the patient enters the fixed bolus corresponding to 10% to 20% of his(her) total insulin daily dose as the meal value in the Pump as instructed by the investigator, and to ensure more globally the patient uses the automated insulin delivery system in a right way.

- From 11th day onwards (after the first CGM sensor change), the family nurse will visit the patient every 3 days.
 - At each visit, the family nurse will:
 - change the Pump catheter and refill the cartridge,
 - control the charge of the battery and charge it if necessary,
 - ensure that the patient enters meal value in the pump,
 - ensure that adverse events and device deficiencies/failure are reported by the patient in his/her diary. Any adverse event and/or device deficiencies/failure must be reported by the family nurse to the HHP. Every 3 visits, the family nurse will change the CGM sensor.
 - o upload data from the Pump to the t:connect® visualisation platform.
- For patients of the control group:
 - The frequency of visit(s) at the patient's home will remain the same as before study initiation, as defined by the medical prescription. In addition to usual diabetes care, the family nurse will ensure that adverse events and device deficiencies are reported by the patient in his/her diary.

The family nurse will immediately inform the investigator of any adverse event occurring during the trial.

- Visit 8 at the patient's home will be planned with the HHP.

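### A 300-unit cartridge on a fixed 3-day refill supplies at most 100 U/day, and no rule shortens the interval for an eligible patient who needs more (minor safety point)

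*Combined protocol and SAP*

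**What the plan says.** **Supply.** Section V.1.1 describes the reservoir as "the t:slim 3mL (300 units) cartridge". Section V.1 restricts the system to two U100 rapid-acting analogues and warns: "Use of insulin with lesser or greater concentration can result in under delivery or over delivery of insulin". A stronger insulin therefore cannot be used to stretch a fill.

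**Interval.** Four places give the same cycle:
- Synopsis, Follow-Up Period: "The family nurse will visit the patient every 3 days for the insulin cartridge refilling".
- V.1.1: "The infusion set will be changed by the family nurse every 3 days at the same time the cartridge is refilled".
- VI.3.3 (initiation): "The family nurse will replace the catheter and refill the insulin cartridge of the Pump every 3 days at home".
- VI.5.3 (follow-up): "From 11th day onwards (after the first CGM sensor change), the family nurse will visit the patient every 3 days", with the cartridge refilled at each of these visits.

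**Dose at entry.** The only limit is selection criterion 7 in IV.1.1: "Total daily insulin dose < 1.5U/kg". The criteria in IV.1.1 to IV.1.3 set no limit in U/day and none on weight or BMI.

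**Monitoring.** VI.5.1 and VI.5.2 keep remote review of glucose and insulin data going through follow-up. VI.5.2 has the pump data uploaded twice a day "during the first 10 days following patient hospital discharge and at each visit afterwards".

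**The concern.** The refill interval is a fixed number of days, while the quantity that empties the cartridge is the daily dose, which is limited only relative to body weight. For an eligible patient with a high absolute dose, following the schedule exactly would leave the pump without insulin before the next planned refill.

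These patients were selected because they need a nurse's daily help with injections or glucose monitoring. In the device arm, nurse contact falls to every third day after the first sensor change. An interruption of delivery in that period would be a safety event for the patient, and a foreseeable one. The risk table in I.4 covers failure of the delivery system but does not list a cartridge that empties early while working as designed.

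**Working it through.** **Inputs from the documents.** Cartridge 3 mL, 300 U, and U100 insulin only (V.1, V.1.1); refill every 3 days (Synopsis, V.1.1, VI.3.3, VI.5.3); entry dose below 1.5 U/kg (IV.1.1).

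**Assumption.** The documents do not give the usable volume after priming or other losses. I use 260 to 300 U as an illustrative range. The 300 U column is the best case and needs no assumption about losses.

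**Step 1, the plan's own figure.** 3 mL × 100 U/mL = 300 U, as stated.

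**Step 2, daily ceiling = usable volume / 3.** 300/3 = 100 U/day; 280/3 = 93.3; 260/3 = 86.7.

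**Step 3, weight at which the ceiling is reached = ceiling / (U/kg).**
- Just under 1.5 U/kg: 100/1.5 = 66.7 kg at 300 U; 86.7/1.5 = 57.8 kg at 260 U.
- At 1.0 U/kg: 100 kg at 300 U; 86.7 kg at 260 U.

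**Step 4, gap before a 72-hour refill = 72 − (usable volume / daily dose) × 24, if nobody refills early.**

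| Pump dose (U/day) | Cartridge lasts, 300 U | Gap, 300 U | Cartridge lasts, 260 U | Gap, 260 U |
|---|---|---|---|---|
| 110 | 65.5 h | 6.5 h | 56.7 h | 15.3 h |
| 120 | 60 h | 12 h | 52 h | 20 h |
| 150 | 48 h | 24 h | 41.6 h | 30.4 h |

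**Step 5, is there a dose rule anywhere?** I looked for a sentence that brings the refill forward at a higher dose and found none. V.4.4 lets a trained caregiver replace devices at home, but it does not mention refilling and sets no dose trigger. Nothing forbids an early refill either.

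**What cannot be computed.** The documents give no distribution of weight or daily dose, and the dose on the pump may differ from the dose at entry. The share of patients above the ceiling is unknown.

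**The case against.** The best counter-argument is that high use would be seen before visits thin out. VI.3 gives 14 days of open-loop pump use (14/3 = 4.7 refill cycles), with home nurse visits kept at their usual daily frequency. The investigator then sets the closed loop from the recorded pump data (VI.4.1). From day 3 to the first sensor change the nurse visits at least twice a day (VI.5.3), and the investigator checks the platform twice a day for the first 10 days (VI.5.1). A patient emptying 300 U in under 72 hours would normally be noticed in that time. Need-based cover also exists: provider visits whenever the patient asks (V.2), consumables sent according to need (V.4.2), round-the-clock technical and medical hotlines, training on alarms, and exclusion of patients who cannot perceive them.

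Most of this stands, and it is why the point is minor. Two cases remain open. One is the patient already known to exceed the ceiling, for whom the text still prescribes 3 days. The other is the patient whose dose rises later. For the second, uploads at visits show what the last cycle used but not a cartridge running out between visits.

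Three stronger readings are tempting and are not supported:
- **That nothing in place prevents depletion.** Whether the pump warns of low insulin is a matter for the user guide, which V.4 cites and which is not part of the documents.
- **That the back-up pen is unavailable for an empty cartridge.** V.8 ties the kit to a component deficiency, but I.4 promises it without that condition and calls it a back-up. Appendix 4 also provides for pen or syringe correction once glucose and ketones are high. The wording is uneven; access is not denied.
- **That the primary comparison is biased.** Nothing in the documents shows how often depletion would occur or that it would move time in range, and the sample size and analysis model are unaffected.

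**Conclusion.** The point holds as a minor patient-safety improvement that is cheap to make. Followed exactly, the stated schedule supplies at most 100 U/day, and the entry criteria admit patients above 66.7 kg who may need more. That figure assumes a full 300 U fill with no loss. With the assumed 260 U the ceiling is 86.7 U/day and the weight 57.8 kg. For a patient above the ceiling the gap runs from several hours (6.5 h at 110 U/day) to a day or more (24 to 30.4 h at 150 U/day), provided nobody refills early. Early observation and the existing support make an unnoticed gap less likely and limit its harm, but they do not correct the written interval. The number of patients affected is unknown and may be small.

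**What to change.** 1. In the Synopsis, V.1.1, VI.3.3 and VI.5.3, replace the fixed refill interval with: *at least every 3 days, and sooner when the patient's recent total daily pump dose would use up the usable cartridge volume (per the user guide) before the next visit, by the family nurse or a trained and validated caregiver*.
2. Before visits drop to every 3 days, have the investigator set each patient's interval from the pump dose already observed, and review it whenever an upload shows a higher dose. As a guide, a 2-day interval covers up to 300/2 = 150 U/day with a full fill, or 260/2 = 130 U/day at the assumed lower volume.
3. In VI.5.3, tie the sensor change to 9 days, as in the Synopsis, instead of to every third nurse visit. Otherwise 2-day visits would move it to 3 × 2 = 6 days and daily visits to 3 days.
4. Optionally, state in V.8 that the back-up pen may be used for an empty cartridge.

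**Cost.** Protocol wording for everyone, and extra refills for high-dose patients only. Day 11 to day 90 is 79 days: every 3 days gives 79/3 = 26.3 refills; every 2 days gives 79/2 = 39.5, so 13.2 more; daily gives 79, so 52.7 more. A trained caregiver can share these, which matters because lower healthcare cost is one of the study's aims (I.3). Before day 11, extra refills can largely use the daily or twice-daily nurse visits already planned. If the user guide requires a new infusion set at each refill, the same number of extra sets is needed. Eligibility, sample size and analysis do not change.

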| Appendix 4- Hyperglycemia and Hypoglycemia protocol instructions | 155 |

LIST OF ABBREVIATIONS AND DEFINITIONS

| | - a | | | | | |
|--------------|---|--|--|--|--|--|
| Abbreviation | Definition | | | | | |
| AE | Adverse Event | | | | | |
| ADA | American Diabetes Association | | | | | |
| ADA | Afficient blubetes Association | | | | | |
| ADE | Adverse Device Effect | | | | | |
| ADR | Adverse Drug Reaction | | | | | |
| ALT | ALanine aminoTransferase | | | | | |
| ANCOVA | ANalysis of COVAriance | | | | | |
| ANSM | Agence Nationale de Sécurité du Médicament et des produits de santé | | | | | |
| АР | Artificial Pancreas | | | | | |
| ASADE | Anticipated Serious Adverse Device Effect | | | | | |
| AST | ASpartate aminoTransferase | | | | | |
| ATC | Anatomical Therapeutic Chemical | | | | | |
| CA | Competent Authority | | | | | |
| CGM | Continuous Glucose Monitoring | | | | | |
| CNEDIMTS | (French) Commission Nationale d'Evaluation des Dispositifs Médicaux et des Technologies de Santé | | | | | |
| CNIL | Commission Nationale de l'Informatique et des Libertés | | | | | |
| CRA | Clinical Research Associate | | | | | |
| CRF | Case Report Form | | | | | |
| CRO | Contract Research Organisation | | | | | |
| CS | Clinically Significant | | | | | |
| CV | Coefficient of Variation | | | | | |

| DRM | Data Review Meeting | | | | | |
|--------|---|--|--|--|--|--|
| DSMB | Data Safety Monitoring Board | | | | | |
| DSIVID | Data Safety Monitoring Board | | | | | |
| EC | Ethics Committee | | | | | |
| ENCC | Echelle Nationale de Coûts à méthodologie Commune | | | | | |
| FDA | Food Drug Administration | | | | | |
| GCP | Good Clinical Practice | | | | | |
| GDPR | General Data Protection Regulation | | | | | |
| HAS | (French) Haute Autorité de Santé | | | | | |
| HbA1c | Haemoglobin A1c | | | | | |
| НСР | HealthCare Provider | | | | | |
| HDL | High-Density Lipoprotein | | | | | |

| ННР | Home Healthcare Provider |
|------|---|
| ICF | Informed Consent Form |
| iCGM | Integrated Continuous Glucose Monitoring |
| ICH | International Council for Harmonisation of Technical Requirements for Pharmaceuticals for Human Use |
| IFU | Instructions For Use |
| IMD | Investigational Medical Device |
| IR | Insulin Resistance |
| ISF | Investigator Site File |
| ITT | Intention To Treat |
| IWRS | Interactive Web Randomization System |

| LDL | Low-Density Lipoprotein |
|--------|--|
| MD | Medical Device |
| MDI | Multi Drug Injections |
| MedDRA | Medical Dictionary for Regulatory Activities |
| MMSE | Mini Mental State Examination |
| MoCA | Montreal Cognitive Assessment |
| NGAP | Nomenclature Générale des Actes Professionnels |
| OAD | Oral Antidiabetic Drug |
| PP | Per Protocol |
| PT | Preferred Term |
| QALY | Quality-Adjusted Life Year |
| QoL | Quality of Life |
| RBC | Red Blood Cell |
| SAE | Serious Adverse Event |
| SAP | Statistical Analysis Plan |
| SD | Standard Deviation |
| SDV | Source Data Verification |
| SEAE | Study Emergent Adverse Event |
| SOC | System Organ Class |
| SOP | Standard Operating Procedure |
| SADE | Serious Adverse Device Effect |
| SUSAR | Suspected Unexpected Serious Adverse Reaction |

| T2D | Type 2 Diabetes | | | | |
|-------|---|--|--|--|--|
| TIR | ime In Range | | | | |
| TMF | rial Master File | | | | |
| UADE | Unanticipated Adverse Device Effect | | | | |
| USADE | Unanticipated Serious Adverse Device Effect | | | | |
| WBC | White Blood Cell | | | | |
| WHO | World Health Organization | | | | |

I - Introduction

I.1 - BACKGROUND

I.1.1 - PATHOPHYSIOLOGY OF TYPE 2 DIABETES

In Type 2 Diabetes (T2D), the pathophysiological process results in an inadequate production of insulin and an inability of the body to respond fully to insulin, defined as insulin resistance (IR). Due to insulin resistance in muscle and liver tissue, the body's ability to metabolize glucose becomes compromised. IR is widely recognized as one of the earliest steps in the progression of T2D. Although a genetic component to this condition exists in many patients, environmental conditions (lifestyle) are thought to be key players in the disease's emergence [8].

One of the characteristic features of T2D is the progressive nature of the disease. In patients with prediabetes and early T2D, the pancreatic beta cells can compensate for insulin resistance by secreting greater amounts of insulin to maintain normal glycaemic control. Prediabetic state turns to a diabetic state as pancreatic beta cells gradually become exhausted and can no longer meet the demands of insulinresistant tissues. Increasing insulin resistance combined with worsening of beta-cell dysfunction, and eventual failure, lead to loss of glycaemic control. The consequence of such continued disease progression is the increased risk of diabetic complications, with macrovascular complications being the most frequent comorbidity associated with T2D. Similarly, microvascular complications, such as neuropathy, nephropathy, or retinopathy, are likely to occur. Moreover, multiple pathophysiologic abnormalities including defects in functioning in α -cells, adipocytes, gastrointestinal tract, kidney, and brain play important roles in the development of glucose intolerance in T2D as well [9].

I.1.2 - EPIDEMIOLOGY OF T2D

Type 2 Diabetes is the most common type of diabetes with a population approximately 10 times larger than the T1D population with a fast growth rate [10]. T2D most commonly affects older adults, but rates of T2D are increasing in children, adolescents and younger adults [10]. Indeed, the prevalence of T2D is strongly associated with aging and obesity. The number of T2D cases is expected to increase in all countries as a result of population aging, changes in dietary habits and a sedentary lifestyle that have led to an increasing prevalence of obesity [1-4]. The World Health Organization (WHO) has estimated that Type 2 Diabetes will affect over 366 million people by 2030 [4]. Given the high mortality associated with the disease, primarily due to macrovascular complications, Type 2 Diabetes is a major public health concern worldwide [11]. Like many other countries in the world, T2D is a major public health issue in France, facing to an increasing number of patients with T2D, and thus an increasing burden of diabetes-related complications [21]. Moreover, diabetes is the principal cause of terminal renal insufficiency, adult-onset blindness and lowerlimb amputation in Western Europe [2].

Improvement in T2D care has led to a significant increase in life expectancy of T2D patients during the last decades [13]. However, a large number of T2D patients do not achieve an optimal HbA1c level.

I.1.3 - BURDEN OF THE DISEASE

In 2014, diabetes was the 4th reason of healthcare expenditure in France with 7.9 Bn € out of a total of 155 Bn€. Diabetes comes after psychiatric diseases, neuro-cardiovascular diseases and cancers. Healthcare

expenses affected 3 Million patients: 83% of expenses were related to primary care, 10% to hospital care and 7% to other care. Expenses directly related to diabetes were of 2.3 M€: antidiabetic drugs at 48%, medical devices (strips, insulin pens and other medicines such as insulin pumps, CGMs) at 35%, and hospitalizations for diabetes as the main reason of admission at 12%. The increase of the prevalence of diabetes in France from 2012 to 2014 was of 2.9% [50].

I.1.4 - T2D TREATMENTS AND CARE

The goal of diabetes treatment is the prevention of the onset and progression of micro- and macrovascular complications, as well as the achievement of quality of life and longevity equivalent to people without diabetes. The UK Prospective Diabetes Study (UKPDS), Diabetes Control and Complications Trial/Epidemiology of Diabetes Interventions and Complications (DCCT/EDIC) and Kumamoto Study [48] have established the importance of glycaemic control [3, 14, 15].

Poor glycaemic control is a significant challenge in the management of Type 2 Diabetes, with 36% to 69% of patients failing to reach glycaemic control targets. These individuals are at an increased risk of developing diabetes-related complications, which impact negatively on their quality of life and have cost implications for healthcare providers [16].

Glucose control in Type 2 Diabetes deteriorates progressively over time, and, after failure of diet and exercise alone, needs on average a new intervention with glucose-lowering agents every 3-4 years in order to obtain/retain good control [17].

The management of the T2D patient is carried out on the front line by the general practitioner. It often requires multidisciplinary cooperation with dieticians, physical activity professionals, nurses, ... Diabetologists and other specialists may be needed.

I.1.5 - INITIAL TREATMENT

As long as a residual beta-cell function is retained, the therapy of T2D is designed to support the natural regulatory system instead of replacing it completely [13]. The treatment of T2D usually starts with oral antidiabetic drugs (OAD). Indeed, if patients are not able to reach their glucose target, they are prescribed the first line of T2D therapy – Metformin. Poor glycaemic control on metformin can lead to dual and even triple therapy where a patient is given an additional (or two additional) therapeutic(s). This can be a SGLT2 inhibitor or an incretin-based therapy (DPP4 inhibitor or GLP1 receptor agonist). If the patient also fails to achieve tight glycaemic control following this, they may expect to be prescribed insulin [18, 19]. Usually one or two daily injections of basal insulin are sufficient for an extended period [20]. The addition of basal insulin improves glycaemic control and achieves the target HbA1c level in over 50-60% of patients.

1.1.5.1 - INTENSIFICATION

For patients who are refractory to basal therapy in addition to previously prescribed antidiabetic agents, treatment intensification requires the addition of prandial insulin therapy to target the control of postprandial hyperglycaemia. The resulting regimen of multiple injections of rapid-acting insulin with basal insulin achieves target glycaemia in > 70% of patients but carries an increased risk of hypoglycaemia and body weight gain. Full compliance with insulin therapy regimens remains challenging, and injection anxiety, quality of life disruption, and discomfort are well documented obstacles [5].

1.1.5.2 - INSULIN PUMP AND CGM

In the OpT2mise trial, it was shown that for insulin-treated T2D patients with unsatisfactory glycaemic control on Multi Drug Injections (MDI) therapy a significant improvement (in terms of HbA1c, but also Time In Range) could be achieved by using an insulin pump [5-7].

In the Diamond trial, it was found that CGM use could help to improve glycaemic control on MDI therapy (HbA1c and Time In Range) for insulin-treated T2D patients [21].

It can be estimated that today T2D patients account for 17 to 20% of the total insulin pump users in France among an estimated total of 60 000 patients in 2018 (extrapolation from Air Liquide Healthcare data through its different affiliates like Orkyn, Vitalaire, LVL, and Dinno Santé). This estimated ratio is unique in Europe and may be explained by existing pump funding for T2D patients in France which is not the case in some other European countries where pump use is only funded for T1D patients.

A higher frequency of treatment discontinuation by T2D patients versus T1D can been observed at 6 months after treatment initiation, as well as 3 years afterwards. Most of treatment discontinuations before 6 months are associated with psychological issues regarding the acceptability of the device. Clearly T1D / T2D patients differ in many ways, and mainly in the fact that most T2D persons are not insulin dependent for several years.

This type of patients is usually older (an average age of 59 years for T2D patients). Therefore, these patients might see the pump as a new constraint associated with a new and invasive step in their disease. Moreover, using this device can induce some stress, for it involves comprehension and an active participation from the patients to make it effectively work. In this regard, it is key to educate patients and to train healthcare professionals, so they can provide the necessary help to ensure the proper and safe use of therapeutic tools, and empower the patients so they can manage their glycaemic control.

1.1.5.3 - CLOSED-LOOP SYSTEMS

The development of a closed-loop system that combines CGM with computer-based algorithm to determine the amount of insulin to be delivered by the pump may provide further improvements in both glycaemic control and reduction in the risk of hypoglycaemia. Hybrid closed-loop systems are characterized by automated insulin delivery system, apart from when the user administers insulin boosts at meal time. Superior control may delay the onset of macro- and microvascular complications of diabetes [22].

Several closed-loop (Artificial Pancreas (AP)) systems have been developed and successfully evaluated in people with type 1 diabetes leading to improved glucose control and less time in hypoglycaemia [23].

Opposed to the multitude of clinical trials in T1D, there is far less data with AP solutions in patients with T2D [24-28]. In those studies, it was found that AP had the potential to significantly improve Time In Range and to reduce time in hyperglycaemia for patients with T2D in hospital settings [13].

A closed-loop insulin delivery system has also been shown to be safe and feasible in insulin-naïve patients with T2D in a controlled research facility setting [28].

1.1.5.4 - OUTCOME MEASUREMENT

The ease and accuracy with which glycated haemoglobin A1c (HbA1c) can be measured has made it an invaluable clinical tool for the evaluation of the treatment effect for patients with diabetes. However, HbA1c has some inherent drawbacks. While HbA1c reflects average blood glucose over the last 2–3 months,

its limitation is the lack of information about acute glycaemic excursions and the acute complications of hypo- and hyperglycaemia events. HbA1c also fails to identify the magnitude and frequency of intra- and interday blood glucose variation [29]. Moreover, HbA1c is unreliable in patients with anemia, haemoglobinopathies or iron deficiency and in female patients who are pregnant [30, 31].

The introduction of CGM has provided an opportunity to develop metrics of glycaemic control that provide valuable information beyond that furnished by glycated haemoglobin A1c (HbA1c). Time In Range refers to the time an individual spends within the glucose target range (70 to 180 mg/dL) [31].

Up to now, HbA1c was considered as the surrogate marker of interest in diabetes.

Despite its perceived clinical value by clinicians and patients alike, the Food and Drug Administration (FDA) has not yet recognized TIR as a valid outcome in order to prove efficacy [32]. In France, the Haute Autorité de Santé (HAS) / Commission Nationale d'Evaluation des Dispositifs Médicaux et des Technologies de Santé (CNEDIMTS) is willing to consider a surrogate endpoint if validated for the prediction of the expected clinical outcome in a scientific paper [33].

Time In Range (TIR) may be used as an appropriate clinical endpoint in diabetes research and as a measure of glycaemic control in patients. Evidence suggests that TIR is inversely correlated to risk of developing vascular complications in patients with diabetes [32]. TIR is associated with the prevalence of diabetic retinopathy and/or microalbuminuria in T2D [21, 31, 32].

